inclusion criteria for phase 1 are (i)  $\geq 55$  years and  $\leq 80$  years old at the time of the visit; (ii) does not already have lung cancer; and (iii) meets 2013 USPSTF smoking criteria for LDCT screening (30+ pack-year smoking history and current smoker or quit in the past 15 years) or may meet the criteria if a complete smoking history were taken. The inclusion criteria for phase 2 are (i)  $\geq 50$  years and  $\leq 80$  years old at the time of the visit; (ii) does not already have lung cancer; and (iii) meets 2021 USPSTF smoking criteria for LDCT screening (20+ pack-year smoking history and current smoker or quit in the past 15 years) or may meet the criteria if a complete smoking history were taken.

*Post-Implementation Provider and Staff Interviews:* Up to 36 providers and staff who participated in the pilot implementation or clinical trial will be included in the interviews.

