### **Aim 3. Evaluation**

*Patient Outcomes Assessment:* up to 21,000 patients will be enrolled. Eligibility criteria are the same as for participation in the pilot implementation and clinical trial.

*Provider and Staff App Usage Assessment:* up to 1,200 providers and staff will be enrolled. Eligibility criteria are the same as for participation in the pilot implementation and clinical trial.

*Provider and Staff Surveys:* Up to 400 providers and staff from University of Utah primary care clinics will be surveyed regarding the intervention. Providers and staff will be eligible if they have interacted with the intervention through the pilot implementation or clinical trial.

*Patient Surveys:* Up to 200 patients from University of Utah primary care clinics will be surveyed regarding the intervention. Patients will be eligible if the intervention was used in their care and they speak English.

*Provider and Staff Focus Groups:* Up to 36 providers and staff will be enrolled in focus groups to evaluate the intervention as well as explore implementation and adoption issues with CDS, SDM, and guideline-focused care in general. Eligibility criteria will be the same as for the provider and staff surveys.

*Patient Focus Groups:* Up to 18 patients will be enrolled in focus groups to evaluate the intervention as well as explore implementation and adoption issues with CDS, SDM, and guideline-focused care in general. Eligibility criteria will be the same as for the patient surveys.

*Stakeholder Interviews:* Up to 100 key stakeholders who implemented the intervention at the University of Utah or elsewhere will be interviewed with a goal of understanding barriers and facilitators to the scalable dissemination of evidence-based CDS, as well as to estimate the associated time and resource costs. Eligibility criteria will be involvement in the implementation of the intervention for clinical care purposes.

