### **Aim 3. Evaluation**

*Patient Outcomes Assessment:* The primary outcome is the proportion of patients eligible for LDCT screening per USPSTF guidelines receiving LDCT screening. Planned secondary outcomes are the expected number of lung cancer deaths prevented given the risk profiles of individuals screened with LDCT, the expected number of major complications given the risk profiles of individuals screened with LDCT, and, if approved by the University of Utah Value Driven Outcomes research committee, the operating margin attributable to study patients during study period (total revenues minus total cost). Data for the operating margin analysis

will leverage the Value Driven Outcomes value analysis tool co-developed by PI [name] to determine the true costs of care.

We will report the number of patients and patient characteristics for each phase of the interrupted time series (ITS) study. We anticipate a 12-month baseline phase, a 9-month intervention phase, and a 9-month enhanced intervention phase which incorporates improvements made to the CDS intervention based on initial experience. We will conduct a segmented regression analysis to fit the monthly series and assess the extent to which the intervention was associated with changes in outcome measures. The study phases constitute three segments of regression models with monthly time points. We will use the segmented least squares approach with parameters for intercept, baseline trend, and changes in the level and trend after the intervention. We will start with assuming a linear trend line within each segment. Nonlinearity trends will be explored if the linear assumption is violated. We will use the Durbin Watson statistic as a measure of autocorrelation and test up to six-order autocorrelation. Potential confounding is limited to covariates associated with the outcome that change at the time of the intervention. We will test for confounding due to changes in study population characteristics such as age, gender and race. Statistical significance will be defined at alpha = 0.05.

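### Eligibility widens from the 2013 to the 2021 criteria at an unstated point in the monthly series, so two secondary totals, and possibly the primary proportion, can move without any effect of the tool

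*Combined protocol and SAP*

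**What the plan says.** In the SAP, Aim 3. Evaluation, the primary outcome is the proportion of guideline-eligible patients who receive LDCT. Two of the secondary outcomes are "the expected number of lung cancer deaths prevented given the risk profiles of individuals screened with LDCT" and "the expected number of major complications given the risk profiles of individuals screened with LDCT". Neither has a denominator. The series has three segments (12 months of baseline, 9 of intervention, 9 of enhanced intervention), and segmented regression is to "assess the extent to which the intervention was associated with changes in outcome measures".

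The Inclusion Criteria for Aim 2 define two trial phases. In phase 1 the patient is aged 55 to 80 and "meets 2013 USPSTF smoking criteria for LDCT screening (30+ pack-year smoking history and current smoker or quit in the past 15 years"). In phase 2 the patient is aged 50 to 80 and "meets 2021 USPSTF smoking criteria for LDCT screening (20+ pack-year smoking history and current smoker or quit in the past 15 years"). For the Patient Outcomes Assessment (Inclusion Criteria, Aim 3), "Eligibility criteria are the same as for participation in the pilot implementation and clinical trial".

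On confounding, the SAP says "Potential confounding is limited to covariates associated with the outcome that change at the time of the intervention" and "We will test for confounding due to changes in study population characteristics such as age, gender and race". Its COVID-19 modifications add a comparison of patient characteristics across the three segments, with propensity matching or weighting if they differ significantly.

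**The concern.** Trial phases 1 and 2 are not dated and not matched to the ITS segments, and no criteria version is given for the baseline months. A natural reading, though not a stated one, is that phase 1 is the intervention segment and phase 2 the enhanced segment. The eligible pool would then widen exactly where the model looks for the effect of the enhancement.

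A total over people screened grows when more people qualify, even if nobody's chance of being screened changes. A proportion moves if the newly eligible are screened at a different rate from the rest. The design has no concurrent control, so the regression cannot separate a guideline change from a tool effect at the same break. What is at stake is a statement about lung cancer deaths prevented, or about a change in screening rate, that partly reflects a new definition of who counts.

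**Working it through.** **Inputs.** From Background and Introduction: the 2021 criteria add 67% to the eligible population and 33% to the mortality benefit. These are not local figures, and applying them here is an assumption. From the SAP: 6.4% screened at present, 12.8% and 20% assumed in the next two segments, at least 900 eligible patients per month, two-sided alpha 0.05.

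**The plan's own figure.** The stated power above 95% reproduces. Comparing one month of 900 with another gives 99.6% (6.4% v 12.8%) and 98.5% (12.8% v 20%); pooled segments give more than 99.9%. That figure concerns the primary proportion only and is not in dispute.

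**Shift in expected deaths prevented with no change in care.** Let y be the benefit per newly eligible person screened relative to the others, and r their screening rate relative to the others.

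- y = 0.33 / 0.67 = 0.49.
- Relative total = 1 + 0.67 × y × r.

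| | y = 0.1 | y = 0.49 | y = 1.0 |
|---|---|---|---|
| r = 1 | +7% | +33% | +67% |
| r = 0.5 | +3% | +16.5% | +33.5% |

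For scale, at fixed yield the planned steps would raise the same total by 12.8/6.4 − 1 = 100% and 20/12.8 − 1 = 56%. The central 33% is a third of the first step and 0.33/0.5625 = 0.59 of the second.

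**Expected complications.** The documents give no relative risk for newly eligible patients. With equal risk and r = 1 the total rises 67%.

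**Primary proportion.** With newly eligible uptake u, the proportion is (0.064 + 0.67u) / 1.67. At u = 6.4% it stays at 6.4%. At u = 2% it is 0.0774 / 1.67 = 4.6%. In that second case r = 0.02/0.064 = 0.31, and expected deaths prevented rise by 0.67 × 0.49 × 0.31 = 10%, so the two outcomes move in opposite directions.

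**Does a denominator alone solve it?** No. Deaths prevented per eligible patient at r = 1 becomes 1.33/1.67 = 0.80 of its former value, a 20% fall with no change in care. Holding the criteria at 2013 in every month removes the shift. Holding them at 2021 in every month does so only if the newly eligible were already screened at the later rate during baseline.

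**Chance of a false significant level change.** Simulation assumptions: 30 months split 12/9/9, no tool effect, widening at month 22 with immediate uptake, y = 0.49, r = 1, monthly volume CV 5%, individual-benefit CV 1, independent months, ordinary least squares, no matching or weighting. The level term at month 22 is significant in about 40% of runs if 6.4% is a monthly rate, and in about 8% if it is an annual rate spread over 12 months. Any of the four change terms is significant in about 46% and 18% respectively, against a background of about 16%. For a rate within 2013-eligible patients, the level term is back at about 5%.

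**The case against.** The strongest reply is that the plan is not silent. It assigns a version to each trial phase and carries that into the outcomes assessment. The baseline is described as pre-pandemic and Purpose and Objectives dates the new guideline to March 2021, so the 2013 version was in force at baseline. That stands: a reader might infer that no rule on criteria exists, and the documents do not support this. What is missing is the match to ITS months. The version in force at baseline is also not the same as a stated rule for classifying records drawn later from the data warehouse.

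A second reply is that matching or weighting comes before the regression, and that ages 50 to 54 would probably trigger it. This stands in part. The list of characteristics is open and the step may remove some of the shift. But it is conditional, and neither pack-years nor criteria version is named. Patients aged 55 or over with 20 to 29 pack-years would remain unless pack-years enters the model.

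A third reply is that the EHR reminders go to guideline-eligible patients, so screening of the newly eligible may itself be partly a tool effect. That is fair, and it is why the totals should be kept as measures of reach and the newly eligible shown separately.

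**Conclusion.** The concern holds as an unstated mapping with a real consequence. If the criteria widen at or near a segment start, both totals can rise and the primary proportion can shift with no change in care. The central figure for expected deaths prevented is +33%, with a range of 7% to 67% over relative yield 0.1 to 1.0 at equal uptake, and about +16.5% at half the uptake. The primary proportion would fall to about 4.6% if newly eligible uptake is 2%. All of this assumes that the national figures in the Background apply locally, and it is before any matching or weighting.

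A reader might go further and infer that the planned test has a false-positive rate near 40%. The documents do not support any single rate. Background and Introduction gives 6.4% as the share screened over a year, while the power statement sets it beside 900 patients per month. The two readings give about 40% and about 8% for the level term, and both depend on noise and speed of uptake that the documents do not specify. Nor do the documents show that the widening does fall at the enhancement; that is possible, not stated.

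**What to change.** State the ITS month in which the 2021 criteria take effect and the version used in every month, including baseline.

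For the primary outcome and both expected-number outcomes, run the segmented regression in patients who meet one fixed criteria set, documented 2013 eligibility, in all three segments. Express the two expected outcomes per 1,000 such patients seen per month. Report patients eligible only under the 2021 criteria as a separate stratum. Keep the overall totals, with eligible counts by segment and criteria version, as measures of reach.

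The cost is a SAP amendment and one dated eligibility flag per patient. The fixed-set analysis omits newly eligible patients and those whose eligibility is only possible because their smoking history is incomplete. It therefore does not credit the tool for reaching them; the separate stratum shows the newly eligible, and the totals describe overall reach.

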To mitigate the impact of pandemic COVID19, we will make the following two modifications in the statistical analysis plan. First, we will redefine the baseline phase so that it has no overlap with the lockdown period, because all the non-essential medical visits have been cancelled during this period. Secondly, we anticipate the patient characteristics and composition during the intervention phase and even enhanced intervention phase might be different from the baseline phase which is observed before the pandemic. We will compare the distributions of patient characteristics across the three phases of the ITS study. If significant discrepancies are observed in the patient characteristics and composition, we will conduct propensity score modeling and use a matching or weighting approach to create a comparable study cohort in each phase before running the originally proposed segmented regression analysis. If any lock-down periods coincide with the intervention phases, we may remove visits occurring during these periods from the analysis.

To estimate statistical power, we followed Rozario, Moore and McWilliams' approach, and used the statistical software SAS. We assumed the proportion of eligible patients receiving LDCT screening, the primary outcome in the study, will increase from the current 6.4% to at least 12.8% during the intervention phase and 20% during the enhanced intervention phase. Empirical EHR data indicate at least 900 patients per month will meet USPSTF LDCT eligibility criteria throughout the study period. With this conservative monthly sample estimation and the length of time at each phase, we would have more than 95% power to detect

the hypothesized differences in the primary outcomes at different phases. All the estimated statistical powers were calculated based on two-sided tests with a significance level of alpha = 0.05.

*Provider and Staff App Usage Assessment:* Utilization metrics will include the number of clinics, providers, and other empowered staff utilizing the intervention.

*Provider and Staff Surveys:* Descriptive data analysis will be conducted and aggregated data will be compared across groups.

*Patient Surveys:* The same methods will be used as for the provider and staff surveys.

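### The COVID-19 rules screen out lockdown time by phase and by visit, but do not protect the period in which a retained patient's LDCT would be done, and no rule assigns a scan to a month

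*Combined protocol and SAP*

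**What the plan says.** All of this is in Statistical Methods, Aim 3. Evaluation, unless another section is named.

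- **Outcome.** "The primary outcome is the proportion of patients eligible for LDCT screening per USPSTF guidelines receiving LDCT screening". No index date, scan window or month of attribution is given.
- **Model.** Segmented least squares on a monthly series, with anticipated phases of 12, 9 and 9 months. The parameters are an intercept, a baseline trend and "changes in the level and trend after the intervention".
- **Baseline rule.** "we will redefine the baseline phase so that it has no overlap with the lockdown period". This moves the phase in calendar time. The reason given is that routine visits had been called off; scans are not mentioned.
- **Later lockdowns.** "If any lock-down periods coincide with the intervention phases, we may remove visits occurring during these periods from the analysis". This rule is optional and works by visit date.
- **Eligibility** (Inclusion Criteria, Aim 2). Age is assessed at the visit, and patients must be seen at a participating clinic.
- **Baseline rate.** The power calculation uses 6.4%. Background and Introduction reports that figure as the share of eligible patients screened in the year before August 2018, which is a 12-month look-back.

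The documents give no lockdown dates, no baseline end date and no visit-to-scan interval.

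**The concern.** A visit and the scan that may follow it are separate events. The protocol allows for delay: Procedures, Aim 2 foresees patients reviewing printed material before a follow-up discussion at a later visit. A baseline that stops the day before the lockdown satisfies the stated rule, yet it can hold patients whose scans would have fallen in the lockdown. If those patients count as unscreened, the shortfall sits in the last baseline months. These points have the most leverage on the baseline slope, and the model projects that slope to launch to obtain the level change. Part of an apparent launch effect could then come from the lockdown. The same gap affects visits shortly before any lockdown inside an intervention phase; there the sign depends on which part of the segment is depressed.

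**Working it through.** **1. The plan's own figure.** Inputs from the power paragraph: 6.4%, 12.8% and 20%; 900 patients a month; two-sided alpha 0.05. Even single months give high power:

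- 6.4% v 12.8%: 0.064 / √[(0.064×0.936 + 0.128×0.872)/900] = 4.64. Then 4.64 − 1.96 = 2.68, so power is 99.6%.
- 12.8% v 20%: the same formula gives 98.5%.
- Pooled phases exceed 99.9%, and a simulation of the 12/9/9 segmented model gives about 100% for both level changes.

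The stated power of more than 95% is reproduced. This point concerns bias, not power.

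**2. How a depressed baseline month enters the level change.** Assume visit-month counting and a scan window that ends inside the lockdown. With baseline months k = 1 to 12, the fitted baseline line at time L gives month k the weight

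w(k, L) = 1/12 + (L − 6.5)(k − 6.5)/143

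Here 143 is the sum of squared deviations of 1 to 12 from 6.5. L = 13 if launch follows directly on the time axis, L = 16 with a 3-month gap, and L = 25 with a 12-month gap. If d(k) is the number of points lost in month k, the level change is inflated by Σ w(k, L) × d(k).

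| Month | w at L = 13 | w at L = 16 | w at L = 25 |
|---|---|---|---|
| 12 | 0.333 | 0.449 | 0.795 |
| 11 | 0.288 | 0.382 | 0.665 |

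**3. Numbers put in.** The true series is flat at 6.4% with no intervention effect. The shares lost are assumptions: 25% of 6.4 is 1.6 points and 50% is 3.2 points.

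| Assumed loss | No gap | 3-month gap | 12-month gap |
|---|---|---|---|
| 25% in month 12 | 0.333×1.6 = +0.5 | +0.7 | 0.795×1.6 = +1.3 |
| 50% in month 12 | 0.333×3.2 = +1.07 | +1.4 | 0.795×3.2 = +2.5 |
| 25% in month 11, 50% in month 12 | 1.07 + 0.288×1.6 = +1.53 | +2.0 | 2.54 + 0.665×1.6 = +3.6 |

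The baseline slope falls by 3.2×5.5/143 = 0.12 points a month in the second row, and by a further 1.6×4.5/143 = 0.05, to 0.17, in the third. The trend-change term rises by the same amounts.

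**4. False-favourable results.** In simulation of the third row (binomial, 900 a month, no gap, no true effect), the level term is significant in favour of the intervention in about 40% of trials; nominal is 2.5%. With a 3-month gap it is about 49%.

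**5. The same lockdown under other counting rules.**

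- Scans counted in the month they occur: baseline months before the lockdown are unaffected, so the bias is nil.
- Open-ended window, with a scan after the lockdown still credited to the visit: nil.
- 12-month look-back, the form in which the 6.4% is reported: baseline months before the lockdown are unaffected. A launch month whose look-back holds, say, 3 lockdown months without scans would show 6.4 × 9/12 = 4.8%, a bias of −1.6 points.

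**The case against.** A reader might infer that the plan cuts by visit date throughout, counts late scans as unscreened, and therefore inflates the launch effect. The documents do not support that.

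- The baseline rule is a calendar redefinition. Only the optional rule for later lockdowns cuts by visit.
- Nothing says that the baseline ends where the lockdown begins. A baseline ending months earlier also fits the text.
- The outcome is nowhere defined as a scan within a set time after an index visit. Fixing age at the visit settles who is eligible; it does not settle how scans are counted.
- The one screening rate whose period is described for this health system is a look-back, under which the launch bias can be downward.
- Scan lag, share of scans lost and gap length are all assumed. The largest figure needs several unstated conditions together.
- The plan will explore nonlinear trends if linearity fails, and a sharp drop at the end of the baseline might be seen there.

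All of this stands as a limit on direction and size. It does not remove the gap. Visit-based eligibility and visit-based removal make visit-month counting a natural reading, and no stated rule excludes it. The linearity check does not guarantee that a one- or two-month dip is found, and it does not say what would follow for the baseline. Without a stated counting rule, the choice that decides whether and how the lockdown biases the primary result could be made after the data are seen.

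**Conclusion.** The concern holds in conditional form. The COVID-19 rules protect phases and visits but leave no buffer for a scan that follows a retained visit, and the outcome has no rule for placing a scan in a month. An upward bias requires all of three things: months indexed by visit, a limited forward window, and a baseline running up to or close to the lockdown. Under those conditions the illustration runs from +0.5 to +1.5 points with months numbered consecutively. It reaches +3.6 points for the two-month loss if a 12-month gap is kept on the time axis, against an assumed first-step effect of 6.4 points. Under the other readings the bias is nil or, at launch, downward. The true size and sign cannot be determined from the documents. The matter should be settled before the monthly series is built.

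**What to change.** In Statistical Methods, Aim 3:

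1. State the month of attribution and one ascertainment window (for example, 90 days after the visit), used identically in all phases.
2. End the baseline at least one window before the lockdown starts, and move the 12-month baseline earlier so that it keeps 12 points.
3. For any later lockdown, exclude all visits whose window overlaps it. "we may remove visits occurring during these periods from the analysis" reaches only visits dated inside it, and is optional.
4. If a look-back measure is used instead, exclude months whose look-back overlaps a lockdown.

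**Cost.** This is a change of wording, with earlier records drawn from the data warehouse the plan already uses. With a 90-day window the baseline is about three months older, and a few more months may be dropped if a lockdown recurs. A 12-month look-back would cost more, because up to 12 months after a lockdown would be affected. Precision is not a serious obstacle. In simulation with a 3-month gap, simply dropping the affected last 1, 2 or 3 baseline months, without replacing them, returns the estimate to 6.4 points and the two-sided false-positive rate to about 5%. Power for the launch level change is then about 100%, 99.7% and 97%.

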LDCT can result in significant harm, with the balance of benefits and harms dependent on the patient's risk profile. The NLST found substantial harms associated with LDCT screening, including high false positive rates (96.4%) which can lead to unnecessary and potentially harmful invasive procedures. Moreover, additional studies found that the balance of benefits and harms is highly dependent on the patient's risk profile. These studies developed validated models for predicting the likelihood of lung cancer, false positive LDCT tests, and adverse events based on patient-specific risk factors including age, gender, smoking history, and asbestos exposure. Among LDCT-eligible patients, the ratio of false positive results to LDCT-prevented lung cancer death range from 1,648 among those in the lowest quintile of risk to 65 for those in the highest quintile of risk.

Shared decision making (SDM) ensures that patients and providers make informed, patient-centered decisions regarding LDCT screening. Because the net benefit of LDCT screening can

vary dramatically across eligible patients, the USPSTF strongly advocates for SDM, asserting that “the decision to begin screening should be the result of a thorough discussion of the possible benefits, limitations, and known and uncertain harms.” In a 2015 decision memo, the Centers for Medicare and Medicaid Services (CMS) required a SDM consultation involving use of a decision aid for payment of initial LDCT screening. SDM is the process wherein the provider shares medical information about options and patients share their values and preferences. Following the sharing of information by both parties, the patient and provider collaborates to decide on the course of action that reflects both the best medical evidence and the patient’s preferences and values.

Current LDCT screening rates among eligible patients is <5% nationally. Despite the USPSTF recommending LDCT in 2013, the percentage of eligible smokers who received LDCT screening in the past 12 months remained low and constant, from 3.3% in 2010 to 3.9% in 2015, and a more recent analysis found no improvements. At University of Utah Health, 6.4% of eligible patients received LDCT screening in year preceding August 2018.

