Following the roll-out, clinic leaders may receive periodic feedback on use of the intervention and LDCT screening rates, including comparisons to other clinics. Clinic leaders may be given user-level data so that outlier performances can be addressed if desired. Activities for facilitating implementation may include regular email, phone, or in-person communication with clinic leaders to discuss CDS adoption and address barriers to adoption; identify “implementation pearls”; and share these “pearls” with other clinics. We and others have shown that such facilitation activities improve the adoption and impact of practice change interventions. Contact frequency will be determined by workflow adoption, with more intensive follow-up directed to clinics with lower adoption rates. We will maintain a log of interactions to identify common issues, and issues will be prioritized and addressed.

*Patient Participation in Clinical Trial:* Patients will be included in the clinical trial if they meet the clinical trial inclusion criteria described earlier.

*Post-Implementation Provider and Staff Interviews:* Early formative interviews will be conducted with care team members at the pilot clinic, and potentially other intervention clinics, as the users respond to the intervention. The purpose is to examine impact on workflow, uncover any usability problems, refine implementation procedures, and identify any training needs. Interviews are expected to take approximately 45 minutes to 1 hour. Audio and screen recordings will be made of the interviews where appropriate with participant consent. Audio-recordings may be transcribed. Screen recording tools may include eye tracking. Some screen captures may include actual patient data. We may record the screen, eye movements, and audio to analyze intervention use by the participant for later analysis or for participants to comment on their thought process as they review their own recordings.

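### Does carrying a one-year screening rate of 6.4% into a monthly segmented regression undermine the claim of more than 95% power?

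*Combined protocol and SAP*

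**What the plan says.** The Background and Introduction gives the source of the baseline: "6.4% of eligible patients received LDCT screening in year preceding August 2018". The Aim 3 part of the Statistical Methods takes that figure as the starting level and assumes that the proportion "will increase from the current 6.4% to at least 12.8% during the intervention phase and 20% during the enhanced intervention phase". It combines this with at least 900 eligible patients a month and phases of 12, 9 and 9 months. It reports power above 95% for differences between phases, computed in SAS by a cited approach whose settings are not reproduced.

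The outcome is defined without a time window: "The primary outcome is the proportion of patients eligible for LDCT screening per USPSTF guidelines receiving LDCT screening". The analysis is a "segmented regression analysis to fit the monthly series", with an intercept, a baseline trend and "changes in the level and trend after the intervention". Two safeguards are added: "Nonlinearity trends will be explored if the linear assumption is violated", and the analysts will "test up to six-order autocorrelation".

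On roll-out, the Procedures (Aim 2) describe a systemwide launch after a pilot and one improvement release at about month 9 of an 18-month trial. They also describe possible contact with clinic leaders, "with more intensive follow-up directed to clinics with lower adoption rates".

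**The concern.** A yearly proportion and a monthly proportion are different quantities, and no conversion is described. A 12-month look-back, which is the time basis of the 6.4%, is longer than either 9-month intervention phase and would turn a sudden change into a slow ramp. Continuing work with slow-adopting clinics could also spread a rise over several months.

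Either way, the first intervention phase acquires an upward slope, and the segmented model judges the enhancement against that slope carried forward. The second transition is where the plan looks for an added effect of the enhancement. If that contrast were weak, power above 95% would promise more than the model can deliver there.

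**Working it through.** **Inputs.** From the documents: 6.4%, 12.8% and 20%; 900 patients a month; 12 + 9 + 9 = 30 monthly points; six regression parameters, so 30 − 6 = 24 residual degrees of freedom; two-sided 5%. Assumed, because the documents do not give them: outcome window, uptake time, repeat counting of patients, and extra month-to-month variation. Results are given as launch / enhancement. Power for the segmented model comes from simulated binomial series fitted by ordinary least squares.

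**1. The plan's own figure, single months.** Standard error = √[p₁(1−p₁)/900 + p₂(1−p₂)/900].
- Launch: √(0.0000666 + 0.0001240) = 0.0138; 0.064/0.0138 = 4.64; 4.64 − 1.96 = 2.68; power 99.6%.
- Enhancement: √(0.0001240 + 0.0001778) = 0.0174; 0.072/0.0174 = 4.14; 4.14 − 1.96 = 2.18; power 98.5%.

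Pooling whole phases (10,800 v 8,100 and 8,100 v 8,100) gives about 100% for both.

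**2. The planned model, immediate monthly steps.** The level change is the new line at its first month minus the old line carried forward to that month. For n months, Sxx = n(n²−1)/12, which is 143 for 12 months and 60 for 9. The variance factors are:
- first month of a 9-month phase: 1/9 + 4²/60 = 0.378;
- a 9-month line carried one month forward: 1/9 + 5²/60 = 0.528;
- the 12-month line carried one month forward: 1/12 + 6.5²/143 = 0.379.

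Standard errors:
- Launch: √(0.379 × 0.0000666 + 0.378 × 0.0001240) = 0.0085; 6.4/0.85 = 7.5.
- Enhancement: √(0.528 × 0.0001240 + 0.378 × 0.0001778) = 0.0115; 7.2/1.15 = 6.3.

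Simulated power for the level change is 100/100%. The stated figure reproduces.

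**3. Gradual uptake.** Suppose both rises are linear over three months.
- The first intervention phase runs 8.53, 10.67, then 12.8 (%). Its mean is 12.09 and its slope is (4 × 4.27 + 3 × 2.13)/60 = 0.39. Carried forward it predicts 12.09 + 5 × 0.39 = 14.04.
- The enhanced phase has mean 19.2 and slope (4 × 4.8 + 3 × 2.4)/60 = 0.44. Its first fitted value is 19.2 − 4 × 0.44 = 17.44.
- The expected level change is 17.44 − 14.04 = 3.40 points instead of 7.2.

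| Uptake | Level change | Joint level and trend |
|---|---|---|
| Both immediate | 100/100% | 100/100% |
| Both over 2 months | 99.9/98.5% | 99.8/95.5% |
| Both over 3 months | 97/72% | 99/54% |
| Both over 4 months | 81/27% | 98/17% |
| Both over 6 months | 34/4% | 99/5% |
| Both over 9 months | 9/8% | 99/10% |

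The loss at the second transition requires both rises to be slow. With a three-month launch and an immediate enhancement, the expected level change is 20 − 14.04 = 5.96 points, or 5.96/1.15 = 5.2 standard errors. Enhancement level power is then above 99%, and it remains so for launches over six or nine months. With an immediate launch and a gradual enhancement, the joint test at the enhancement keeps 92 to 96%.

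The nine-month case also shrinks the assumed effect. Its phase means are 6.4 + 6.4 × 5/9 = 10.0% and 12.8 + 7.2 × 5/9 = 16.8%.

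**4. A 12-month look-back.** With monthly rates of 6.4/12, 12.8/12 and 20/12 (%), the first intervention phase climbs to 9 × 1.067 + 3 × 0.533 = 11.2% by its last month. Launch is still found as a trend change (93%). At the enhancement, level power is 22%, trend 16% and joint about 24%. These figures treat months as independent although the windows overlap.

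**5. Repeat counting.** If each patient enters k monthly denominators a year, the monthly proportions are the yearly ones divided by k. With immediate steps, level power is 97.4/95.1% at k = 2.8, 73/71% at k = 6 and 41/45% at k = 12. At k = 12 a pooled phase comparison still has 98.3/90.8%. The documents do not fix k.

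**6. Extra month-to-month variation, immediate steps.** An added standard deviation of 1.0, 1.5 or 2.0 points gives 99.9/99.7%, 97/97% or 88/88%. With lag-1 autocorrelation of 0.4 as well, 1.5 points gives 94/94% and 2.0 points gives 81/82%.

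**The case for a change.** The best case for a change does not need the figure to be wrong. The 6.4% is plainly annual, the model is plainly monthly, and nothing in the text links them. Values reached at some time during a phase, together with continuing facilitation, fit a gradual rise at least as well as a jump. A phase-mean comparison would keep its power under gradual uptake, but it is not the analysis described. Nor does the loss come only from a smaller assumed effect: if the ramps over three to six months are rescaled so that phase means stay at 12.8% and 20%, level power at the enhancement is still only 63%, 16% and 7% for three, four and six months.

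The sensitivity of the second contrast therefore stands. Three things limit it.

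- The weak scenarios are chosen, not read from the plan. No section proposes a 12-month look-back or states an uptake time. A systemwide launch after a pilot, and a single dated improvement release, fit a fairly prompt step as well.
- The obvious remedies trade one loss for another. If a 60-day outcome window were used and months crossing a phase boundary left out, level power would be 95/87% with the yearly proportions halved and 81/71% with one third of them. Dropping the first two months of each intervention phase restores 100/99% under three-month uptake on the unscaled values, but gives up 4 of 18 intervention months. A roll-in and an outcome window each use up months, so combining them costs more again. No choice is best in every scenario.
- A restated percentage would probably change little in the conduct of the trial. The roll-out is systemwide, the duration is set, and the patient count is what primary care supplies.

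**Conclusion.** The concern identifies real omissions but not a power figure shown to be wrong. On the direct reading, with monthly levels reached at once, level power is about 100% at both transitions. It stays above 95% with two-month uptake in both phases, with up to about 2.8 repeat denominators per patient (about 2.4 if the fit is weighted), or with an extra between-month standard deviation of 1.5 points and no autocorrelation.

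It falls well below the claim at the second transition only if both rises take three months or more, if a 12-month look-back is used, or if patients are counted many times a year. The documents state none of these.

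The missing window, contrast and uptake assumption are details that competent analysts must fix before a monthly series can be fitted. The plan already provides for checking linearity and autocorrelation once the data are seen. Which window or roll-in to use is a trade-off, not a correction. No change to the plan is required. Anyone reading a null second contrast should bear in mind that it is the more fragile of the two if uptake at launch and after the enhancement both prove slow.
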